#### ***Analysis***

Data from this pilot study will be descriptive with outcomes being estimates of variables relating to feasibility . Sample characteristics will be described as frequencies for categorical variables and means for continuous variables. HEI-2015 scores will be summarized as means and standard deviations and percent maximum score [(mean score/maximum score) x 100%]. We will explore intervention effects on change in HEI score from baseline to 12 weeks using a two-sample *t*-test. Although we will likely not have enough power, we will conduct exploratory analyses to assess differences in HEI scores among low vs. high engagers using linear regression. Similar analysis will be conducted for changes in relevant behavioral and psychosocial variables.

If the distribution of any outcome is heavily skewed, we will either appropriately transform the data so it's normally distributed or use a generalized linear mixed model with an appropriate link function. Sensitivity analyses will fit linear mixed models with a full maximum likelihood estimation using all available data to allow for responses to be missing at random, where the missing mechanism may be related to either observed covariates or response variables, but not related to the unobserved data. All analyses will be conducted using STATA 14 (StataCorp, College Station, TX).

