### ***Recruitment***

The target enrollment is 50 participants in accordance with published guidance for pilot studies and to allow for drop-outs. We partnered with two different entities for participant recruitment, using different strategies. The first is a private, non-profit health system that operates Federally qualified community health centers in North Carolina that also administer WIC benefits. During WIC encounters, WIC nutritionists (n=2) will upload the name, phone number and email address of WIC beneficiaries who are interested in joining the pilot into a secure online Duke Box folder. Research assistants will upload this information into REDCap (Research Electronic Data Capture), a secure, web-based software platform designed to support data capture and management for research studies. The second recruitment entity is the WIC office from the 2nd most populated county in North Carolina. This county WIC office will include flyers in mailings sent to all new WIC recipients. These flyers will provide information about the pilot study and will include a QR code that caregivers can scan to take them directly to the screener.

Additionally, the Nutrition Services Branch within the North Carolina Division of Public Health, which implements the WIC program for North Carolina, will alert all WIC directors in the state of the pilot study via email. The email will include the flyer with the QR code for WIC directors to distribute throughout their WIC clinics as they see fit. We will also utilize social media platforms, such as Facebook, and Duke University websites to distribute information about the study and aid in recruitment. Interested caregivers can also find a link to the screener from a study-specific website, <https://healthyrootsstudy.com>. This website contains study and contact information for the research team.

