### ***Screening, baseline assessments, and enrollment***

All study related processes will be completed electronically to aid in the dissemination potential. Surveys are administered through REDCap, allowing caregivers to self-guide themselves through each one. The system incorporates functions such as scheduling surveys and tracking completion. If surveys are not complete, the system will automatically send reminders, via SMS text message and email, for up to 7 days.

The first survey is the eligibility screener which includes questions regarding eligibility criteria, as described above. As soon as contact information is entered into REDCap by the research

assistant the system will automatically email a link to the online screener and send a SMS text the following day if not complete. Interested caregivers will also be able to access the screener by scanning the QR code on the flyer or clicking on the screener link found on the study website and Facebook page. If the caregiver is eligible, they will confirm their contact information and be directed to an online consent form (see Figure 2 for study flow). Once the consent form is electronically signed, caregivers will be directed to complete an online baseline survey.

Upon completion of the baseline survey, participants will be asked via email to complete two 24-hour dietary recall assessments administered through the Automated Self-Administered 24-Hour Dietary Assessment Tool (ASA24). The ASA24 is a freely available, web-based, self-administered tool developed by the National Cancer Institute and provides comprehensive nutrient data on all foods and beverages consumed during the previous 24-hour period. Caregivers will be asked to complete two separate 24-hour dietary recalls (1 week and 1 weekend day) within two weeks of each other. When both ASA24s are complete caregivers will be enrolled in the intervention.

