Once the participant is enrolled, they will begin receiving SMS text messages. The first text message will include a web link to a study-specific YouTube channel that includes an orientation video. This 2-minute orientation video informs participants of what to expect including surveys they have to complete and incentives for completing those surveys. They are presented with the study schedule and contact information for the study team and encouraged to reach out with any questions or concerns. Subsequently, participants will receive their first goal, followed by a new goal every 2 weeks until the end of the study for a total of 6 goals. During each 2-week goal cycle, participants will receive 3 tips per week related to that goal. At the end of each week, they will receive a tracking message related to their assigned goal. If they respond, they will receive feedback on their progress. If they do not respond they will receive an automated reminder. If still no response, they will receive a reminder to track next time as well as a tip. After 12 weeks, participants will be asked to complete two more ASA24s and a satisfaction survey. Participants will receive a gift card after completion of each ASA24 (n=4) for a maximum amount of \$55.

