### ***Analytic Approach***

#### ***Primary Outcomes***

*Implementation* will be assessed through intervention engagement calculated by dividing the number of days with valid tracking data (numerator) over the total number of possible tracking days (denominator). We will calculate and compare engagement rates by week. We will create a dichotomous outcome variable comparing high vs. low engagers using an established cutoff of 80% or more engagement in weekly self-monitoring . Bivariate analyses using *t* tests and chi-square will be used to examine predictors of intervention engagement. Poisson regression with a robust variance will be used to examine sociodemographic differences among those with higher levels of engagement (80% or more weeks of tracking) and estimate risk ratios and 95% confidence intervals.

*Preliminary efficacy* will be measured by assessing changes in diet quality. Dietary intake will be measured using the ASA24 recall tool. Participants will be asked via email to complete 2 separate dietary recalls (1 week and 1 weekend day) within a 14-day period prior to enrollment and again upon study completion, for a total of 4 dietary recalls. These data will be used to calculate a Healthy Eating Index-2015 (HEI) score, which consists of 13 components, 9 of which assess adequacy of the diet, including 1) total fruit; 2) whole fruit; 3) total vegetables; 4) greens and beans (including peas); 5) whole grains; 6) dairy; 7) total protein foods; 8) seafood and plant proteins; and 9) fatty acids, which is a ratio of poly- and mono- unsaturated to saturated fatty acids. The remaining 4 assess dietary components recommended to be consumed in moderation: 10) refined grains; 11) sodium; 12) added sugars; and 13) saturated fats . For all components, higher scores reflect better diet quality as moderation components are reverse scored. Each component is scored on a density basis rather than absolute scores, either as a percentage of calories or per 1000 calories allowing use of the HEI for a range of ages and populations. Summed scores of the 13 components yield a maximum total score of 100, with a higher score reflecting greater compliance with the 2015–2020 Dietary Guidelines for Americans .

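### The SAP names a two-sample t-test for HEI change in one group measured twice; it should name a paired analysis, since ignoring positive within-person correlation costs power.

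*SAP*

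**What the plan says.** The SAP lists change in diet quality, measured by the HEI-2015 score, as preliminary efficacy under Primary Outcomes. Under Analysis it states: "We will explore intervention effects on change in HEI score from baseline to 12 weeks using a two-sample" t-test. The next sentence deals with engagement: "we will conduct exploratory analyses to assess differences in HEI scores among low vs. high engagers using linear regression". It then says that similar analysis will be applied to changes in behavioral and psychosocial variables. For missing data it adds: "Sensitivity analyses will fit linear mixed models with a full maximum likelihood estimation using all available data".

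The design behind these analyses has one group. Protocol, Screening, baseline assessments, and enrollment: "When both ASA24s are complete caregivers will be enrolled in the intervention"; and at follow-up, "After 12 weeks, participants will be asked to complete two more ASA24s and a satisfaction survey". The SAP (Primary Outcomes) agrees that each participant is asked for two recalls "within a 14-day period prior to enrollment and again upon study completion, for a total of 4 dietary recalls". Neither document describes a control arm, randomization or a second sample.

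The SAP also sets the level of ambition: "Data from this pilot study will be descriptive with outcomes being estimates of variables relating to feasibility".

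**The concern.** A two-sample t-test assumes two independent groups. Here the baseline and 12-week scores come from the same mothers, so each pair is expected to be positively correlated. The variance of a mean within-person change falls as that correlation rises, and the two-sample formula ignores this.

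Three things are at stake.

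- **Precision.** A real improvement could be reported with an unduly wide interval and called non-significant only because the pairing was dropped.
- **Planning a later trial.** The SAP promises means and SDs of HEI scores but not the SD of the within-person change. A later trial needs that SD, and it cannot be recovered from the two time-point SDs alone.
- **Spread.** The plan to analyze other change variables in a similar way may carry the same test to them.

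There is also a separate wording point. Without a comparison group, the result is a pre-post change, and calling it an intervention effect claims more than the design supports.

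**Working it through.** **Which two samples could be meant?** There are three readings.

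1. Baseline scores against 12-week scores, treated as independent groups. This is the literal reading of the test name in a single-group study.
2. High against low engagers, compared on change. The next SAP sentence gives the engager contrast to linear regression, and a contrast between engagers is not naturally called an intervention effect, so this reading fits poorly.
3. Loose wording for two time points, with a paired test intended. This would be harmless, but the text does not say it.

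The arithmetic below applies to reading 1.

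**Inputs.** Target enrollment is 50, including an unquantified allowance for drop-out (Protocol, Recruitment). The SAP gives no power, SD, correlation, effect size or alpha for this test, so there is no planned figure to reproduce. Assumptions: SD 12 HEI points at both times, n = 40 mothers with both scores, a gain of 5 points, two-sided alpha 0.05, and within-person correlation ρ from 0 to 0.7.

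**Standard errors of the mean change.**

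- Two-sample: SD × √(2/n) = 12 × √(2/40) = 2.68, whatever ρ is.
- Paired: SD × √(2(1 − ρ)/n). At ρ = 0.5 this is 12 × √(1/40) = 1.90.
- Ratio of two-sample to paired: 1/√(1 − ρ).

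**P-value for an observed 5-point gain.** Two-sample: t = 5/2.68 = 1.86 on 78 df, p = 0.066 at every ρ. Paired at ρ = 0.5: t = 5/1.90 = 2.64 on 39 df, p = 0.012.

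**Smallest observed gain with p < 0.05.** This is the critical value times the SE. Two-sample: 1.991 × 2.68 = 5.3 points. Paired at ρ = 0.5: 2.023 × 1.90 = 3.8 points. The same numbers are the half-widths of the 95% CI.

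**Type I error and power.** Two-sample figures come from simulated bivariate-normal data (400,000 samples per setting for ρ = 0, 0.3, 0.5 and 0.7; 100,000 for ρ = 0.2). Paired power comes from the noncentral t distribution.

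| ρ | SE ratio | Two-sample type I error | Power, two-sample | Power, paired | p, paired (5-point gain) | Smallest significant gain, paired |
|---|---|---|---|---|---|---|
| 0 | 1.00 | 5.0% | 45% | 44% | 0.070 | 5.4 |
| 0.2 | 1.12 | 2.9% | 45% | 53% | 0.044 | 4.9 |
| 0.3 | 1.20 | 2.0% | 44% | 58% | 0.032 | 4.5 |
| 0.5 | 1.41 | 0.65% | 44% | 73% | 0.012 | 3.8 |
| 0.7 | 1.83 | 0.06% | 42% | 91% | 0.002 | 3.0 |

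**Check with other assumptions.** With 50 pairs and a change of 0.4 SD, two-sample power stays at about 0.51, against paired power of 0.59, 0.65, 0.79 and 0.95 at ρ = 0.2, 0.3, 0.5 and 0.7. At ρ = −0.2, an unlikely case, the direction reverses and the two-sample type I error is 7.3%.

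**Drop-out, which pairing does not solve.** Illustration: n = 50, no true change, logit of completion = 0.9 + 0.55 × baseline z-score (about 70% complete). Bias in the estimated change, in HEI points:

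| Analysis | ρ = 0.3 | ρ = 0.5 | ρ = 0.7 |
|---|---|---|---|
| Paired, completers only | −1.3 | −0.9 | −0.6 |
| Two-sample, all available scores | +0.6 | +0.9 | +1.3 |
| Maximum-likelihood random-intercept model | within 0.03 of zero | within 0.03 of zero | within 0.03 of zero |

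The completion model is invented for illustration. It shows only why the planned mixed model should be kept alongside the paired test.

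**The case against.** The strongest reply is that the harm depends on a reading the SAP does not force. Two-sample may be shorthand for two time points, in which case the analyst would run a paired test and lose nothing. Or the t-test may be meant for change by engagement group, since the SAP uses t tests before regression for its engagement outcome. On that reading the figures above do not apply, and the fault is that no pre-post test is named. Neither reading can be excluded, but both still require the sentence to be rewritten.

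The size of the loss is also open to challenge. Each HEI score rests on two recall days, and day-to-day variation lowers the correlation. At ρ = 0.1 and 0.2 the SE ratio is only 1.05 and 1.12, and paired power is 48% and 53% against about 45%. The contrast of 42% with 91% belongs to the top of the assumed range. This stands: the loss may be modest.

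The planned mixed model would largely repair the problem if participant is the grouping factor, which is the natural choice. But it is a sensitivity analysis introduced for missing data, and the participant term is not stated.

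Finally, this is a descriptive pilot. No decision rule depends on the test, and the target of 50 does not come from a power calculation: "The target enrollment is 50 participants in accordance with published guidance for pilot studies and to allow for drop-outs". That limits the severity, but it does not make the named test suit the data.

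**Conclusion.** The concern holds. The documents describe one group measured twice, and the test named for HEI change is one for independent groups. Confidence in the mismatch is high. The size of the consequence is uncertain, because it rests on an assumed SD, number of completers, gain and, above all, within-person correlation. There is no loss at zero correlation, a small one at 0.1 to 0.2, and a large one at 0.5 or more, where the standard error is too wide by a factor of at least 1.41. With positive correlation, false positives are not inflated, and the mean change is the same when the same completers are used at both times. The point should be fixed, at moderate priority: it concerns an outcome listed under Primary Outcomes, but the analysis is exploratory and the error is conservative.

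**What to change.** In the SAP, Analysis section:

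1. Replace the two-sample t-test with the mean within-person change in HEI (12 weeks minus baseline), its SD and 95% CI, and a paired t-test.
2. Apply the same to the other change variables covered by the similar-analysis sentence.
3. Keep the full-maximum-likelihood linear mixed model and state a participant random effect.
4. Describe the result as a pre-post change and not as an intervention effect.
5. If a t-test of change between high and low engagers was intended, say so separately and name the two groups.

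The cost is a few lines of SAP text before analysis. No extra data or participants are needed.

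### HEI change in one group measured twice is assigned a two-sample t-test; a paired analysis is needed, with the planned mixed model specified and reported beside it

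*SAP*

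**What the plan says.** The SAP puts preliminary efficacy under Primary Outcomes, where it "will be measured by assessing changes in diet quality", scored by the HEI-2015 from two recalls before enrolment and two at study completion. For the test, the Analysis section says: "We will explore intervention effects on change in HEI score from baseline to 12 weeks using a two-sample" *t*-test. The next sentence deals with engagement separately: "we will conduct exploratory analyses to assess differences in HEI scores among low vs. high engagers using linear regression". The section then extends similar analysis to changes in behavioural and psychosocial variables.

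On missing data, the same section says: "Sensitivity analyses will fit linear mixed models with a full maximum likelihood estimation using all available data", under missing at random. It gives no fixed effects and no covariance structure for these models. It also sets the status of the results: "Data from this pilot study will be descriptive with outcomes being estimates of variables relating to feasibility".

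In the Protocol (Screening, baseline assessments, and enrollment), every eligible mother who finishes both baseline recalls enters the intervention. Later, "After 12 weeks, participants will be asked to complete two more ASA24s and a satisfaction survey". No control group or randomisation is described. The Recruitment section sets a target of 50 and expects some drop-out.

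**The concern.** A two-sample *t*-test compares two independent groups. Here the baseline and 12-week scores come from the same mothers, and the one HEI comparison that does involve two groups has its own method. So the named test has no two independent samples to work on.

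An analyst following the sentence literally would compare baseline scores with 12-week scores as if they came from different people. The positive covariance between a mother's two scores would be left out of the standard error, and the interval for mean change would be too wide. The main product of a pilot is its estimates and their precision, so a later trial could be planned from a misleading interval. Because similar analysis is planned for other change variables, the same wording could carry the error to them.

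**Working it through.** **Inputs.** From the documents: one group, two time points, 50 mothers, baseline recalls required for enrolment, some drop-out expected. The documents state no power, SD, correlation, drop-out rate or alpha, so there is no figure of the plan's own to reproduce. Assumed here: SD 12 at both times, r = 0.5 (range 0.1 to 0.7), drop-out 0 to 30%, true change 5 points for power, two-sided 5%.

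**Step 1: complete data (n = 50).** Two-sample SE = SD × sqrt(2/n) = 12 × sqrt(2/50) = 2.40. Paired SE = SD × sqrt(2(1-r)/n). The ratio is 1/sqrt(1-r).

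| r | Two-sample SE | Paired SE | Ratio |
|---|---|---|---|
| 0.1 | 2.40 | 2.28 | 1.05 |
| 0.3 | 2.40 | 2.01 | 1.20 |
| 0.5 | 2.40 | 1.70 | 1.41 |
| 0.7 | 2.40 | 1.31 | 1.83 |

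The point estimate is the same by either test; only the SE differs.

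**Step 2: random drop-out.** Let m mothers return 12-week recalls. Run literally, the test compares 50 baselines with m follow-up scores.

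- SE that the test reports: SD × sqrt(1/50 + 1/m).
- True SD of that difference: SD × sqrt(1/50 + 1/m - 2r/50), because each of the m completers contributes to both means.

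At 20% drop-out (m = 40) and r = 0.5:

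- Reported: 12 × sqrt(0.020 + 0.025) = 2.55 (simulated mean 2.54).
- True: 12 × sqrt(0.045 - 0.020) = 1.90. The excess is 34%.
- Paired SE on the 40 completers: 12 × sqrt(2 × 0.5/40) = 1.90.
- 95% half-widths: 1.987 × 2.55 = 5.06 two-sample; 2.023 × 1.90 = 3.84 paired.
- Type I error: 2 × P(Z > 5.06/1.90) = 0.8% (simulated 0.9%).
- Power for 5 points: two-sample P(Z > (5.06 - 5)/1.90) = 49%; paired, by noncentral *t*, 73%.

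Over drop-out 10 to 30% and r from 0.3 to 0.7, the excess runs from 15% (30%, r = 0.3: 2.645/2.295) to 72% (10%, r = 0.7: 2.466/1.431). At r = 0.1 and 20% drop-out it is 5% (2.546/2.430).

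**Step 3: drop-out that is not random.** Simulation, 40,000 trials per setting, n = 50, SD 12, r = 0.5, 30% drop-out, logistic completion slope 1.0 per SD. Bias in points:

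| Completion depends on | Paired, completers | Two-sample, literal | Likelihood, all data |
|---|---|---|---|
| Baseline HEI | -1.53 | +1.51 | -0.02 |
| Unseen 12-week HEI | +1.52 | +3.03 | +2.36 |

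Coverage of the 95% interval, in the same column order, is 88 / 96 / 95% in the first row and 88 / 85 / 79% in the second. Under milder inputs (20%, slope 0.5, baseline-driven) the RMSE is 1.99 paired, 2.01 two-sample and 1.87 likelihood. The likelihood column is a regression-based estimate under unstructured covariance.

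**The case against.** The best defence is that the wording is loose and a paired or change-score analysis was meant. Under a change-score reading the interval is not too wide. But a set of change scores from one group is one sample, so the named test cannot be run on it. The SAP should name the test it intends.

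Three further points stand and limit the concern. The error is conservative, so it creates no false claim of efficacy. The SAP calls the data descriptive and this test exploratory. The size rests wholly on assumed inputs: each time point has only two recalls, so r could be low, and at r = 0.1 with 20% drop-out the paired half-width (5.15) is no narrower than the two-sample one (5.06), because it uses completers only.

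A reader might infer that the mixed model must become the main estimate. The documents do not support that. A paired test repairs the pairing error by itself with almost the same precision: under random 20% drop-out at r = 0.5, simulated half-widths are 3.82 paired and 3.77 by likelihood, and power is 73% and 74%. Which is less biased depends on why mothers drop out, and nothing in the documents settles that. The gift card for each recall should also limit drop-out ("Participants will receive a gift card after completion of each ASA24 (n=4) for a maximum amount of" $55). The all-available-data model would be reported in either case.

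The one-group design is inferred, since the words single arm do not appear and the study-flow figure is not shown. Nothing visible points to a second group.

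**Conclusion.** The concern holds as a mismatch between test and design. One group measured twice calls for a paired analysis, and the two-sample test as named ignores the pairing. Under the literal reading the SE is too large for any positive r: by about a third at r = 0.5 and 20% random drop-out, by 15 to 72% over r of 0.3 to 0.7 and drop-out of 10 to 30%, and by about 5% at r = 0.1. These sizes depend on the assumed correlation and drop-out, the half-widths and power also on SD 12, and the power on a 5-point change. The direction needs only a positive correlation.

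The consequence is moderate: an imprecise interval for an outcome listed as primary but analysed as exploratory, not a wrong confirmatory conclusion. The choice between the paired test and the mixed model as main estimate is a trade-off and not part of the error. The model removes bias if drop-out depends on baseline HEI. It is more biased than the completers' paired change if drop-out depends on the unseen 12-week HEI.

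**What to change.** In the SAP (Analysis), replace the two-sample *t*-test by a paired *t*-test on HEI change, reported as mean change with a 95% CI, and apply the same to the other change variables. This costs a wording change and no new data.

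Beside it, report the mixed model that is already planned, on all enrolled mothers. Specify a time effect and a within-person covariance, and state that the estimate relies on missing at random. Prefer REML or a small-sample correction: in a simulation of 15,000 trials at r = 0.5 and 20% random drop-out, full maximum likelihood with normal limits gave 94.2% coverage against 95.2% for the paired test, a small shortfall that is easily avoided. This takes a few lines of specification, because the SAP now gives neither the effects nor the covariance.

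If the team prefers the mixed model as the main estimate, that is acceptable. The SAP should then say why and keep the completers' paired change as the check.

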#### ***Data collection and outcome assessments***

Self-reported sociodemographic characteristics, including education, age, BMI (kg/m^2), marital status, employment, depression, race, and ethnicity will be collected prior to enrollment through REDCap online surveys (Table 2). REDCap will also be used to capture intervention retention defined as responding to weekly tracking surveys. REDCap will also be used to capture post-intervention satisfaction survey. Research staff will follow up with phone calls and text messages for those who do not complete the satisfaction survey.

**Table 2:** Schedule of Assessments

| Measure               | Screening | Baseline | 12 weeks |
|------------------------------|------------------|-----------------|-----------------|
| Inclusion/exclusion criteria | X                |                 |                 |
| Informed consent             | X                |                 |                 |
| Sociodemographics            |                  | X               |                 |
| Food insecurity  |                  | X               |                 |
| WIC shopping habits          |                  | X               | X               |
| Depression       |                  | X               |                 |

|                                      |  |   |   |
|--------------------------------------|--|---|---|
| Everyday Discrimination  |  | X |   |
| ASA24 Dietary Tracking               |  | X | X |
| Satisfaction Survey                  |  |   | X |

2-item screen for food insecurity

Personal Health Questionnaire Depression Scale (PHQ-8)

Expanded Everyday Discrimination Scale

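### The SAP plans to analyse change in psychosocial variables, but Table 2 of the protocol measures every listed psychosocial scale at baseline only

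*SAP*

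**What the plan says.** The Analysis section of the SAP first sets out the diet analysis: "We will explore intervention effects on change in HEI score from baseline to 12 weeks using a two-sample *t*-test". It then plans an exploratory regression of HEI scores on low versus high engagement, and goes on: "Similar analysis will be conducted for changes in relevant behavioral and psychosocial variables". It does not name the variables meant.

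In the protocol, the section on data collection and outcome assessments says of the background measures: "marital status, employment, depression, race, and ethnicity will be collected prior to enrollment through REDCap online surveys (Table 2". Table 2, in the same section, marks the PHQ-8, the Everyday Discrimination scale and the food-insecurity screen at baseline and leaves their 12-week cells empty. The account of study flow, under the heading on screening, baseline assessments and enrollment, describes follow-up thus: "After 12 weeks, participants will be asked to complete two more ASA24s and a satisfaction survey".

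**The concern.** The SAP uses change to mean the difference between baseline and 12 weeks, then extends that kind of analysis to psychosocial variables. The protocol schedules no second measurement of any such variable. If both documents are followed as written, the analysis has no data.

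The stakes are modest, but part of the loss is permanent: a 12-week score cannot be collected once the 12-week survey has passed. If the investigators want psychosocial change, the schedule gives it up. If they do not, the SAP promises a result that can never be reported, and a later reader may take its absence for selective reporting.

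**Working it through.** The plan states no figure to reproduce here. The check is a count of scheduled time points, compared with what a change score requires.

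**Requirement.** For participant *i*, change = (value at 12 weeks) − (value at baseline). Both terms must be scheduled.

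**Schedule.** Table 2 has 9 rows:

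| Row | Baseline | 12 weeks | Change score possible |
|---|---|---|---|
| Eligibility criteria | – | – | no (screening only) |
| Consent | – | – | no (screening only) |
| Sociodemographics | X | – | no |
| Food insecurity | X | – | no |
| WIC shopping habits | X | X | yes |
| Depression (PHQ-8) | X | – | no |
| Everyday Discrimination | X | – | no |
| ASA24 | X | X | yes |
| Satisfaction survey | – | X | no |

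**Counts.**
- Rows with a 12-week mark: 3 of 9 (WIC shopping habits, ASA24, satisfaction survey).
- Rows with both marks: 2 of 9 (WIC shopping habits, ASA24).
- Psychosocial rows among those two: 0. That is 0 of 2 scales (PHQ-8, Everyday Discrimination), or 0 of 3 with food insecurity.
- Participants able to have a psychosocial change score: 0 of the target 50, since the second value is scheduled for nobody.

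**Cross-check against the text.** The data-collection section places depression before enrollment, in agreement with the table. The study-flow account mentions no psychosocial scale after 12 weeks.

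**Does the reading of the SAP sentence matter?** The promised similarity could refer to the *t*-test or to the comparison of low and high engagers. The sentence concerns changes in either case, so both readings need the 12-week value.

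**Could the sensitivity analysis rescue it?** No. The mixed models in the SAP are meant for responses missing at random among those scheduled. Here no follow-up response exists for anyone, so there is nothing from which to estimate a change.

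**The case against.** The strongest reply is that this is half of one generic sentence in a pilot whose data the SAP calls descriptive. The sentence names no variable or hypothesis, and no main result changes if the psychosocial half is simply not run. The documents never label a measure psychosocial, and the protocol lists depression among the sociodemographic characteristics. The word relevant leaves the choice of variables open, and the contents of the satisfaction survey are not described.

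Much of this is fair as to weight. Treating the PHQ-8 and Everyday Discrimination as the psychosocial scales is an inference, though a natural one. The study-flow account is also weak support: it omits WIC shopping habits, which Table 2 does schedule at 12 weeks, so its silence proves little. The statement about collection before enrollment covers depression only. For the other scales the case rests on Table 2 alone.

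None of this removes the conflict. Table 2 is clear enough to carry it: it marks two measures at both times, so the empty cells elsewhere carry meaning. A free choice of relevant variables cannot supply a second value when no candidate is scheduled twice. Nothing in the documents says that the satisfaction survey repeats a scale; if it is meant to, Table 2 should show it.

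**Conclusion.** The concern holds. The SAP commits to a psychosocial change analysis that the protocol's schedule cannot deliver: 0 of 2 listed scales, or 0 of 3 with food insecurity, are measured twice. The behavioural half of the commitment stands, through WIC shopping habits. Measuring the scales once is a legitimate design choice; it is the SAP wording that conflicts with it.

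The reach is limited. The analysis is exploratory, and 0 of the 2 primary outcomes (engagement and HEI change) are affected. The conclusion assumes that Table 2 lists all scheduled measures and that the psychosocial variables meant are among those it names. It should be corrected, but it does not threaten the main results.

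**What to change.** Make the two documents agree in one of two ways.

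**(a) If psychosocial change is wanted.** Name the scales in the SAP, give each a 12-week mark in Table 2, and attach them to the online survey already planned for that time. This works only if it is done before participants reach week 12; the documents do not state how far the trial has progressed. As an illustration, the PHQ-8 and the food-insecurity screen would add about 8 + 2 = 10 self-administered items. The 2 is stated under Table 2; the 8 is assumed from the scale's name. Everyday Discrimination could be added in the same way, but its length is not given. The cost is a slightly longer survey, perhaps slightly lower completion, and some addition to work already planned: "Research staff will follow up with phone calls and text messages for those who do not complete the satisfaction survey". No extra visits are needed.

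**(b) If it is not wanted.** Limit the SAP sentence to change in WIC shopping habits, and use the baseline-only scales to describe the sample or as candidate predictors of engagement. The Primary Outcomes section already provides for bivariate analyses that "will be used to examine predictors of intervention engagement", but it does not name the predictors, so the scales should be listed there. This costs wording only.

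Under either option, analyse change from baseline to 12 weeks as paired data. The protocol has a single group ("When both ASA24s are complete caregivers will be enrolled in the intervention"), so the same people give both values, and the two-sample test named for HEI should not be carried over to this comparison. Adding WIC shopping habits to the study-flow account of the 12-week assessments would be a useful clarification, nothing more.
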